7.4 Outliers

No formal outlier tests are planned. Normally distributed values that are outside 3 standard deviations from the mean will be queried and verified with source prior to database lock. Tukey's 3-inter-quartile range (IQR) principle² for outlier detection will be utilized for identifying extreme values in platelet count and laboratory measures. Values outside 3 times of 5th and 95th quantile range will be considered as extreme values. If extreme values are present, a sensitivity analysis will be performed after removing the extreme values.

7.5 Derived and Computed Variables:

Patient's age (in years) at randomization is a derived field in the remote capture database, which is rounded to an integer value after subtracting date of birth from the randomization date and dividing the results by 365.25 days.

Change from Baseline

For the continuous variables or variables with linear transformation (e.g. EORTC score), the change at follow-up will be calculated by subtracting the value on screening visit from that on the follow-up visit (week 8 or end of study visit, as appropriate). Percent change will be computed as $(\text{post-value} - \text{pre-value})/\text{pre-value} * 100$.

8 Statistical Analyses

8.1 Enrollment and Disposition

Subject enrollment and disposition will be illustrated on a flow diagram (following CONSORT format) showing the randomization assignment, any possible loss to follow-up, and the ITT, PP and Safety population. Data will be described using incidence rates (number of patients, number

of events, and percent). A table showing enrollment by site and country will be provided. This table will include the number of patients randomized, the number completing each dosing cycle, and major reason for discontinuation, grouped by treatment arm.

A listing of all patients discontinued from the study after randomization with specific reason for discontinuation, cumulative dose (for the Xilonix™ group), and duration on study before discontinuation, broken down by enrolling site and treatment group will be provided.

8.2 Patient Characteristics and Baseline Comparisons

The ITT, PP and safety populations will be used for analysis of demographic and baseline findings. Data will be summarized for each treatment group, i.e. Xilonix™ and placebo arm. Descriptive analysis will be performed summarizing age, gender, Eastern Cooperative Oncology Group (ECOG) status, co-morbidities, body mass index (BMI), cancer therapy, and other relevant baseline risk factors by treatment group. Baseline biochemistry, hematology data will be summarized in separate tables.

The number and percentage of patients reporting prior therapies will be provided by type of therapy (surgery or radiation).

Medication start and stop date will be compared to the date of first infusion of study drug, and will be classified as Prior, Prior and Concomitant, or Concomitant. The number and percentage of patients using prior, prior and concomitant, and concomitant antineoplastic medications will be presented by treatment group. WHO Drug Dictionary, September 2016 will be used for coding of concomitant medications

Continuous variables will be reported as mean \pm standard deviation (SD), median, inter-quartile range (IQR), and minimum and maximum values. The categorical variables will be reported as number of cases (n) and percentage. The baseline characteristics will be compared across the treatment groups for overall difference by using independent-samples t-test for continuous variables and Fisher's exact for categorical data. Normality of the analysis variables will be tested using Shapiro-Wilks test. If the Shapiro-Wilks test is significant, continuous data will be compared using Wilcoxon (for paired data) and Mann-Whitney nonparametric test. A two-tailed p value of <0.05 will be considered statistically significant for the descriptive summary statistics.

8.3 Protocol Compliance and Follow-up

A summary of scheduled visit compliance will be provided by treatment groups. The frequency distribution of drop outs and early terminations will be provided.

Protocol deviations will be grouped into major categories based on relation to exclusion, inclusion criteria, and conduct of trial, and will be summarized by enrolling centers. The categorization will be completed prior to unblinding.

8.4 Efficacy Evaluation

The primary efficacy analysis will be conducted for the ITT and PP population, as defined in section 6.1. Patients will be grouped according to randomized treatment.

8.4.1 Primary Efficacy Endpoint

Subjects who are alive at the data inclusion cutoff date for the analysis will be censored at that date and survival time will be defined as time from randomization to censor date. Patients lost to follow-up and untraceable for survival status will be censored on the last date subject was known to be alive or lost to follow-up. A censoring variable will be created identifying a censored observation. The primary endpoint, overall survival, will be summarized by Kaplan-Meier method and compared between the treatment groups using an un-adjusted log-rank test. The median survival, and cumulative survival probability along with 95% confidence interval (CI) calculate by log-log transformation and 25th and 75th percentiles will be reported according to randomization arms. Kaplan-Meier curves will be generated plotting the estimated survival density function over time. Number of patients at risk on various time intervals will be presented on the curve. The type I error rate to be used for determining statistical significance of the primary outcome is defined in section 5.1 “Interim Efficacy Analyses”.

The primary efficacy analysis will also be conducted for the PP population.

A secondary supportive analysis will be performed comparing survival probabilities across treatment groups, stratified separately by age (dichotomizing at median), gender, ECOG performance status, KRAS mutation status and prior treatment with regorafenib, and number of prior antineoplastic therapies. Survival probabilities and 95% CI for the 25th, median and 75th percentiles will be reported by treatment groups and stratum. No multiplicity adjustment will be made for this supportive analysis.

Another supportive analysis will include a multivariate Cox proportional hazards regression (CPH) method assessing independent predictors of OS after adjusting for potential confounders. Selection of covariates will primarily be based on *a priori* knowledge, and include age (continuous scale), prior cancer therapy (number of regimens will be entered on continuous scale), ECOG performance status (2 categories ECOG 0 and 1 pooled together, and ECOG 2), and KRAS mutation status (coded as no=0, yes=1), and baseline body mass index (BMI). Covariates may be excluded from model if the number of patients representing 1 level of that variable is insufficient. A backward selection method will be used for variable selection; the p-value threshold will be set at 0.10. The proportional-hazard assumption will be tested by Schoenfeld residual analysis. The hazard ratio (HR) and 95% Wald confidence interval (CI) for the HR will be computed and presented in the results. The CPH analysis will be exploratory in nature.

8.4.2 Secondary Effectiveness Endpoints:

LBM: LBM change will be compared across treatment groups both by responder analysis and assessing absolute change.

Patients showing stabilization or improvement from baseline (≥ 0 kg change) will be considered LBM responders and those experiencing LBM reduction will be defined as non-responders. Patients not having a second evaluation for going off the study or any other reason will be considered non-responders. LBM response rate will be compared using Pearson chi-square test. Proportion by group, relative risk and odds ratio estimates will be presented with Cochran-Mantel-Haenszel (CMH) 95% confidence intervals (95% CI).

Absolute change will be compared between treatment groups using an analysis of covariance (ANCOVA) method (SAS GLM procedure) with treatment groups as the factor and baseline value as covariate. The difference in least-square means and 2-sided P values will be derived from the ANCOVA model.

EORTC: Longitudinal and descriptive analysis will be performed to assess patient reported outcomes (PRO). The EORTC survey results will be converted to domain specific scores using the prescribed algorithm (Appendix A). Scores on the EORTC QLQ-C30 functional and symptom scales will be summarized according to the randomization groups. The EORTC survey responses will be converted to domain specific scores using the prescribed algorithm. Scores on EORTC QLQ-C30 functional and symptom scales will be summarized according to the randomization groups. Descriptive statistics of PRO score will be summarized by treatment group.

Patients showing stabilization or improvement from baseline (≤ 0 change) on any two of the three symptom scales (pain, fatigue, appetite loss) will be considered EORTC responders. Patients experiencing reduction or worsening on the symptom scales will be defined as non-responders. Patients missing the follow-up assessment will be considered non-responders. The comparison of responder rate and absolute change will be performed similar to as described for LBM.

Clinical Response Rate: Patients responding on LBM (≥ 0 kg change from baseline) and EORTC (≤ 0 change on any two three symptoms) will be considered Clinical Responders. Patients missing follow-up status will be considered non-responders. Clinical Response Rate will be compared using a Pearson chi-square test. Proportion by treatment groups and relative risk estimates will be presented with CMH 95% confidence intervals.

Platelet Count: Change in platelet count from baseline to follow-up will be compared between treatment groups using the ANCOVA method described above. The last visit cycle where at least 20 patients per group are on study will be used for follow-up data cut-off for this measure. Trend line plots displaying the median platelet count over time (visit cycles) by treatment groups will be generated.

Progression Free Survival (PFS): PFS will be compared by Kaplan-Meier method using log-rank test. Kaplan-Meier plots by treatment arm will be produced, and point estimates and 95% CIs will be summarized.

Objective Response Rate (ORR): The RR will be estimated by dividing the total number of patients with confirmed complete response (CR) and partial response (PR) by the total number of patients in the ITT population. Best overall response (BOR), determined from the sequence of cycle responses assessed, will be used for analysis purposes. Response rates will be compared between treatment groups using a Pearson Chi-square test and Wald 95% confidence intervals for the response rate in each treatment groups will be calculated.

Disease Control Rate (DCR): The DCR will be estimated by dividing the total number of confirmed CRs, PRs and stable disease (SD) by the total number of patients in the ITT population. DCR will be analyzed as described for ORR. Best overall response (BOR), will be used for DCR analysis. DCR will be analyzed as described for ORR.

Inferential analysis for the secondary endpoints, without multiplicity correction, will be carried out separately for stratification variables (age, prior therapy, ECOG performance status, KRAS mutation status, and prior regorafenib treatment status), One-way ANOVA and Fisher's exact tests will be used to compare differences across stratification groups. Proportions by treatment group along with 95% CI will be reported.

A two-tailed p value of <0.05 will be considered statistically significant for all secondary endpoints. SAS 9.2 or higher (SAS Institute Inc., Cary, NC) will be used for statistical analysis.

8.4.3 Additional Exploratory Analyses:

Additional analyses will be performed comparing the primary overall survival endpoint, the secondary endpoints, and incidence of SAE, between Clinical Responders and Non-responders. The statistical methodology in conducting these analyses will follow the same described in the primary and secondary efficacy analysis and safety analysis sections.

8.4.1 Pharmacodynamics (PK) analysis:

PK samples will be tested by XBiotech laboratory for a randomly selected patient population as defined in the study protocol. Descriptive statistics of PK parameters will be presented in a table format. The summary will include average MABp1 concentration at visit cycles along with the standard deviation and coefficient of variation (CV).

8.4.2 Analysis of Safety Outcomes:

The assessment of the safety profile will be based on adverse events, vital signs, physical examinations, and clinical laboratory measurements. All randomized subjects, will be included in the safety analysis.

Exposure duration will be summarized by treatment groups and presented in a table format. Exposure duration will be calculated as Last infusion date – C1D1 infusion date.

Adverse events will be grouped by System Organ Class (SOC) and Preferred Term (PT) within SOC according MedDRA coding dictionary (version 18.0). The number of subjects reporting at

least one adverse event by PT will be summarized across treatment groups. AEs will be summarized by SOC and PT, by relatedness to study treatment and age group. Tables summarizing PT by CTCAE grade and narratives for serious adverse events (SAE) will be presented for each treatment group. A listing of all adverse events by treatment group will be included in the appendix section.

The numbers and percentages of patients experiencing any adverse event (AE) and any serious adverse event (SAE) will be summarized per treatment group will be compared using Chi-square test. The numbers and percentages of patients experiencing any adverse events will also be summarized by maximum severity and relatedness to study treatment per treatment group. Clinical laboratory tests (hematology and chemistry) data will be listed for each subject. Laboratory data will be summarized by Xilonix™ and placebo group. Values outside the normal reference range will be flagged as high or low on the listings. Summary statistics for baseline, on-treatment and change from baseline values will be provided by treatment group in table format. Statistical process control charts showing baseline and post-baseline visit values in comparison with laboratory reference values will be provided for tests of interest.

Vital signs listings (include temperature, pulse, and blood pressure) for each subject will be provided in the appendix section of the Clinical Study Report. Summary statistics by treatment groups will be presented in tabular format.

9 List of Planned Tables

- Randomization by study site, stratified by country
- Subject disposition (all enrolled subjects) with reason for discontinuation, cumulative dose (for Xilonix™ group), and duration on study before discontinuation, broken down by treatment group
- Major protocol deviations (all enrolled subjects)
- Baseline demographic and clinical characteristics by treatment group (per-protocol population)
- Baseline demographic and clinical characteristics by treatment group (ITT population)
- Baseline laboratory data by treatment group (per-protocol population)
- Baseline laboratory data by treatment group (ITT population)
- Listing of patients excluded from efficacy analysis, with reason for exclusion
- Primary endpoint (overall survival) summary by treatment group (count and percent, median survival) (ITT and PP population)
- Secondary endpoints (LBM, platelet count, and EORTC score): summary of change by treatment group: baseline, follow-up, and change with confidence intervals (ITT population and PP population).
- SAE by treatment group (all randomized patients)
- Adverse events (counts, percent) by MedDRA preferred term by treatment group
- Detail listing of adverse events by treatment group (all randomized patients)
- Summary of vital signs and change from baseline over visits (all randomized patients)

- Exploratory summary on pharmacodynamics (PK) analysis findings (patients in Xilonix arm)
- Exploratory summary on Clinical Response Rate analysis findings (patients in Xilonix arm)

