8.3 Overall Risk and Benefit Assessment

Chemotherapy and radiotherapy in the context of advanced metastatic or unresectable colorectal cancer is largely palliative—meaning that complete eradication of the tumor is not expected. The primary goal in this setting is reducing symptomatic effects of the tumor for as long as possible. Due to toxicity, however, these treatment modalities are poorly suited for this objective. Even with the most recent agents (such as multi-kinase inhibitors) treatment related morbidity often results in discontinuation of therapies—ultimately leading to uncontrolled progression and death. New agents that exhibit anti-neoplastic activity and provide improvement in tumor related symptoms are vitally needed to treat this and other advanced cancer populations.

Specific antagonism of IL-1 α through Xilonix™ therapy is viewed as a unique, broad acting tumor suppression strategy that encompasses significant activity to ameliorate symptoms associated with the disease, as well as improve overall survival. IL-1 α is unique in its involvement in so many processes related to tumor progression and collateral symptomatic effects of malignancy. The excellent safety and tolerability profile of the agent make it an ideal treatment option in advanced stage disease, particularly where the use of cytotoxic or other therapies with considerable toxicity are not supported by the risk benefit profile.

Blocking IL-1 α appears to normalize the metabolic energy balance with the net accumulation of lean body mass (LBM). An average LBM increase of 1.9 \pm 2kg was seen in 70% of patients treated ($p < 0.001$) compared to their baseline values. These same patients had improvements in pain, anorexia, and fatigue as measured by the EORTC-QLQ-C30. Traditional, radiographic evidence of anti-tumor activity was also noted, with 21% of patients having stable disease for 3 months or greater, including a partial response in a patient with metastatic colorectal cancer. Additionally, colorectal cancer patients with improvements in LBM had a trend towards a clinically significant overall survival benefit.

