Objective Response Rate (ORR): The ORR will be estimated by dividing the total number of confirmed complete response (CR) and partial response (PR) by the total number of patients randomized. Exact 95% confidence intervals for the response rate in each treatment arm will be calculated. Best overall response (BOR), determined from the sequence of cycle responses assessed, will be used for analysis purposes. Response rates will be compared between treatment groups using a Pearson Chi-square test and Wald 95% CI will be reported.

Disease Control Rate (DCR): The DCR will be estimated by dividing the total number of confirmed CRs, PRs and stable disease (SD) by the total number of patients randomized. DCR

will be analyzed as described for RR. Best overall response (BOR), will be used for DCR analysis. Proportion of response category by group along with 95% CI will be reported.

Inferential analysis for the secondary endpoints, without multiplicity correction, will be carried out for stratification variables (age, prior therapy, ECOG performance status, KRAS mutation status, Regorafenib and bevacizumab failure status), One-way ANOVA, and Fisher's exact tests will be used to compare differences across stratification groups. Proportion by group along with 95% CI will be reported.

A two-tailed p value of <0.05 will be considered statistically significant for all secondary endpoints. SAS 9.2 or higher (SAS Institute Inc., Cary, NC) will be used for statistical analysis.

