Relative Risk (95% CI)	X.XX (X.XX to X.XX)	

7) Clinical Response Rate by Treatment Groups PP Population:

XBiotech USA, Inc., Protocol 2012-PT023 V3.6

Interim Analysis #X, Data Date: ddmmmyyyy

	Xilonix+BSC	Placebo+BSC
N	XXX	XXX
Clinical Response, n (% , 95% CI)	XX (XX, XX-XX)	XX (XX, XX-XX)
Difference (effect size)	XX%	
P value from Pearson Chi-Square test (one-tailed)	0.01	
Relative Risk (95% CI)	X.XX (X.XX to X.XX)	

8) Objective Response Rate by Treatment Groups ITT Population:

	Xilonix+BSC	Placebo+BSC
N	XXX	XXX
Objective Response, n (% , 95% CI)	XX (XX, XX-XX)	XX (XX, XX-XX)
Difference (effect size)	XX%	
P value from Pearson Chi-Square test (one-tailed)	0.01	
Relative Risk (95% CI)	X.XX (X.XX to X.XX)	

9) Objective Response Rate by Treatment Groups PP Population:

	Xilonix+BSC	Placebo+BSC
N	XXX	XXX
Objective Response, n (% , 95% CI)	XX (XX, XX-XX)	XX (XX, XX-XX)
Difference (effect size)	XX%	
P value from Pearson Chi-Square test (one-tailed)	0.01	
Relative Risk (95% CI)	X.XX (X.XX to X.XX)	

10) Disease Control Rate by Treatment Groups ITT Population:

	Xilonix+BSC	Placebo+BSC
--	-------------	-------------

XBiotech USA, Inc., Protocol 2012-PT023 V3.6

Interim Analysis #X, Data Date: ddmmyyyy

N	XXX	XXX
Disease Control Rate, n (% , 95% CI)	XX (XX, XX-XX)	XX (XX, XX-XX)
Difference (effect size)	XX%	
P value from Pearson Chi-Square test (one-tailed)	0.01	
Relative Risk (95% CI)	X.XX (X.XX to X.XX)	

11) Disease Control Rate by Treatment Groups PP Population:

	Xilonix+BSC	Placebo+BSC
N	XXX	XXX
Disease Control Rate, n (% , 95% CI)	XX (XX, XX-XX)	XX (XX, XX-XX)
Difference (effect size)	XX%	
P value from Pearson Chi-Square test (one-tailed)	0.01	
Relative Risk (95% CI)	X.XX (X.XX to X.XX)	

12) Secondary Endpoints Results: Change from Baseline

	Placebo+BSC (n= xxx)			Xilonix+BSC (n= xxx)			P*
	Baseline Mean (95% CI)	Follow-up Mean (95% CI)	Change LS Mean±SE	Baseline Mean (95% CI)	Follow-up Mean (95% CI)	Change LS Mean±SE	
Platelet, 1000/cu mm	XXX±XXX	XXX±XXX	X.XX±X.XX	XXX±XXX	XXX±XXX	X.XX±X.XX	0.XXX
PRO: Global QOL Score	XXX±XXX	XXX±XXX	X.XX±X.XX	XXX±XXX	XXX±XXX	X.XX±X.XX	0.XXX
PRO Symptom Score: Pain	XXX±XXX	XXX±XXX	X.XX±X.XX	XXX±XXX	XXX±XXX	X.XX±X.XX	0.XXX
PRO Symptom Score: Fatigue	XXX±XXX	XXX±XXX	X.XX±X.XX	XXX±XXX	XXX±XXX	X.XX±X.XX	0.XXX
PRO Symptom Score: Appetite	XXX±XXX	XXX±XXX	X.XX±X.XX	XXX±XXX	XXX±XXX	X.XX±X.XX	0.XXX
Lean Body Mass, kg	XXX±XXX	XXX±XXX	X.XX±X.XX	XXX±XXX	XXX±XXX	X.XX±X.XX	0.XXX

13) All Adverse Events by CTCAE Grade

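### The SAP replaces the protocol's exact per-arm intervals for ORR and DCR with Wald intervals, and its table shells print a one-tailed p-value under a two-tailed rule

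*SAP*

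**What the plan says.** **Per-arm interval.** Protocol 10.4, under Objective Response Rate, has two separate sentences. The first concerns each arm: "Exact 95% confidence intervals for the response rate in each treatment arm will be calculated". The second concerns the comparison: "Response rates will be compared between treatment groups using a Pearson Chi-square test and Wald 95% CI will be reported". DCR is handled in the same way as the response rate.

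SAP 8.4.2 has one sentence in their place. It keeps the Pearson test but continues: "using a Pearson Chi-square test and Wald 95% confidence intervals for the response rate in each treatment groups will be calculated". No exact interval remains. For DCR the SAP says "DCR will be analyzed as described for ORR", so DCR inherits the Wald interval. Shell 8 prints the row "Objective Response, n (% , 95% CI" without naming a method, so the SAP text decides which interval is programmed.

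**P-value.** SAP 8.4.2 states: "A two-tailed p value of <0.05 will be considered statistically significant for all secondary endpoints". Protocol 10.4 sets the same rule. SAP 3.2 lists ORR and DCR as secondary endpoints 5 and 6. Yet shells 8 and 9 (ORR, ITT and PP) and 10 and 11 (DCR, ITT and PP) all carry the row "P value from Pearson Chi-Square test (one-tailed". Shells 6 and 7, for the exploratory Clinical Response Rate, carry the same label.

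**The concern.** The SAP appears to have merged the protocol's two sentences, moving Wald from the comparison to the arms and losing the exact interval. The SAP text available gives no reason. The Wald interval does badly when events are few: it can have zero width, run below zero, or cover the true rate much less often than 95%. Patients here are refractory and one arm receives placebo, so low response counts are possible.

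On the second point, when the result favours the drug a one-tailed p is half the two-tailed p. Printed beside a 0.05 rule meant for two-tailed values, it invites a claim that the plan does not allow. Two secondary endpoints are at stake. Overall survival is not.

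**Working it through.** No published figure in the plan depends on this point, so there is nothing to reproduce first. The check compares the texts (above) and computes what follows.

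**Inputs.** Arm sizes are 400 and 200 (SAP 5, Protocol 10.3). The documents give no expected ORR or DCR, so true rates from 0.5% to 50% are assumed to show the range. The only objective response reported for colorectal cancer comes from the pilot, "including a partial response in a patient with metastatic colorectal cancer" (Protocol 8.3). The denominator is not stated. Protocol 1.5 gives 14 colorectal patients out of 52 in all. On those assumed denominators the rate is 1/14 = 7% (exact 0.2 to 33.9%) or 1/52 = 1.9% (exact 0.05 to 10.3%). A rate of 2% or less is therefore possible but not established.

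**Intervals.** With p = x/n, Wald is p ± 1.96·√(p(1−p)/n). Exact (Clopper-Pearson) has lower limit Beta(0.025; x, n−x+1) and upper limit Beta(0.975; x+1, n−x), with a lower limit of 0 when x = 0.

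| Responders | Wald 95% | Exact 95% |
|---|---|---|
| 0/200 | 0.0 to 0.0% | 0 to 1.8% |
| 0/400 | 0.0 to 0.0% | 0 to 0.9% |
| 2/200 | −0.4 to 2.4% | 0.1 to 3.6% |
| 10/200 | 2.0 to 8.0% | 2.4 to 9.0% |
| 20/400 | 2.9 to 7.1% | 3.1 to 7.6% |

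For 2/200: p = 0.01, √(0.01×0.99/200) = 0.00704, and 0.01 ± 1.96×0.00704 gives −0.0038 to 0.0238.

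**Coverage.** For each assumed true rate, add the binomial probabilities of every x whose interval contains that rate.

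| True rate | Wald, n=200 | Wald, n=400 |
|---|---|---|
| 0.5% | 63% | 86% |
| 1% | 87% | 91% |
| 2% | 91% | 90% |
| 5% | 93% | 93% |
| 7% | 93% | 94% |
| 30% | 94% | 95% |

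Exact coverage is at least 95% at every rate in the table, for both arm sizes.

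**Zero-width interval.** The chance of no responders among 200 is (1−p)^200: 37% at 0.5%, 13% at 1% and 2% at 2%.

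**P-value label.** Suppose 120/400 respond on drug and 46/200 on placebo (30% v 23%). The pooled rate is 166/600 = 0.2767. The standard error is √(0.2767×0.7233×(1/400+1/200)) = 0.0387, so z = 0.07/0.0387 = 1.81. The one-tailed p is 0.035 and the two-tailed p is 0.071.

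**False claims for the drug.** If the printed one-tailed p were judged at 0.05, the critical z would be 1.645 instead of 1.960. Summing over both binomials under equal true rates (400 v 200), the chance of declaring the drug better is as follows.

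| True rate in both arms | One-tailed p<0.05 | Two-tailed p<0.05, drug better |
|---|---|---|
| 0.5% | 0.6% | 0.04% |
| 1% | 3.1% | 0.7% |
| 2% | 4.5% | 1.9% |
| 30% | 4.9% | 2.4% |
| 40% | 5.0% | 2.5% |
| 50% | 5.0% | 2.7% |

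**The Pearson test.** Its size at two-tailed 0.05 is 4.2, 4.0, 4.8, 5.1 and 5.1% at true rates of 0.5, 1, 2, 5 and 7%. There is no case for replacing it.

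**The case against.** The best reply has five parts.

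- **The shells are interim templates.** SAP 5.1 calls them interim shells, many pages are headed as an interim analysis, and they still contain placeholders. SAP 9 lists no ORR or DCR table, and interim stopping rests on survival alone. All true. But no other ORR or DCR shells are shown, so the label is likely to carry into the final tables, and the two-tailed rule has no interim exception.
- **The text already governs.** A careful reader can double a p-value that is openly labelled one-tailed. That stands, and the inflation above arises only if someone compares the printed value with 0.05. It does not justify printing a value that does not match the rule.
- **The Wald harm depends on a low ORR.** It does. The one pilot response came from an uncontrolled study assessed by RECIST and says nothing about placebo. The per-arm interval is descriptive, and the count is printed beside it. These points limit the size of the problem. They do not remove the departure from the protocol.
- **The protocol's Wald sentence is loose.** It does not say which quantity the Wald interval is for, and reading it as the difference between arms is an inference. The exact per-arm sentence needs no inference.
- **Restoring the per-arm interval leaves a gap.** Shells 8 to 11 show a difference with no interval, so the protocol's Wald interval for the comparison would still have no place in the tables. This is a fair addition and is taken up in the fix.

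**Conclusion.** Both conflicts are real and follow from the text alone. The SAP's per-arm Wald interval contradicts the protocol's exact one for ORR, and through it for DCR. The one-tailed label in shells 8 to 11 contradicts the two-tailed rule in both documents.

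The numerical effect of the interval is large only if the true ORR is about 2% or lower, which is an assumption. At 5% the limits differ by about 0.2 to 1.0 percentage points, and for DCR near 30% the effect is negligible. The label roughly doubles the chance of a false claim for the drug at rates of 30 to 50% (from 2.4–2.7% to 4.9–5.0%), but only if the printed p is read against 0.05.

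This should be corrected, with high confidence. It does not touch the primary survival conclusion or the sample size.

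**What to change.** - **SAP 8.4.2:** specify an exact (Clopper-Pearson) 95% interval for the response rate in each arm, for ORR and for DCR. Keep the Pearson chi-square test for the comparison.
- **Shells 8 to 11:** relabel the p-value row as two-tailed and name the interval method in the per-arm row.
- **Shells 6 and 7:** align the label for consistency. The Clinical Response Rate is exploratory and outside the secondary-endpoint rule, so this is optional.
- **To match Protocol 10.4 fully:** state that the Wald interval belongs to the between-arm difference, and give it a place beside the difference in shells 8 to 11.

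The main change is one sentence and six labels, using a standard software option. The exact intervals are slightly wider. Data collection, sample size and the primary analysis do not change.
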